Multiple doses of up to 900 mg daily for up to 10 days and single doses of 1200 mg have been examined in healthy subjects. Vadarustat demonstrated dose-proportional PK and dose-dependent serum EPO concentrations that returned to baseline levels with treatment cessation. A higher incidence of adverse events (AEs) in the gastrointestinal System Organ Class (SOC) – nausea, diarrhea, abdominal pain, dyspepsia – was observed in groups treated with 700, 900, or 1200 mg compared with lower vadarustat doses or placebo. Most AEs were mild to moderate, short-lived (1 or 2 days), and assessed as unrelated by investigators. No AEs led to study withdrawal, and no serious adverse events (SAEs) were reported in healthy subjects. No clinically meaningful changes or abnormalities in vital signs, safety laboratory studies, or electrocardiogram (ECG) parameters were reported.

A 16-week, open-label, multicenter, Phase 2 study evaluated vadarustat in 94 subjects receiving chronic hemodialysis previously maintained on epoetin alfa and intravenous (IV) iron from the 3 months prior to Screening. Epoetin alpha was discontinued and subjects were assigned to 1 of 3 vadarustat dose cohorts: 300 mg QD, 450 mg QD, or 450 mg TIW. Dosing was fixed for the first 8 weeks; for the subsequent 8 weeks dose was adjusted from 150 to 600 mg according to Hb response based upon a dose adjustment algorithm. Sixty-nine of the 94 subjects completed the study. The primary endpoint was the mean Hb concentration change from pre-treatment average (Screening Visit 1 [SV1], Screening Visit 2 [SV2], and Baseline Visit) to mid-study (Weeks 7 to 8) and end-of-study (Weeks 15 to 16) and was analyzed using observed Hb values (no imputation for missing data). No statistically significant mean change in Hb from pre-treatment average was observed for either of the 2 time points for any of the three treatment groups.

Among subjects randomized to an initial dose of 300 mg QD, 450 mg QD, or 450 mg TIW, 0% (0 of 30), 3% (1 of 33), and 19% (6 of 31) of subjects withdrew from the study due to worsening anemia, respectively. In a sensitivity analysis using last observation carried forward for the primary efficacy endpoint, no significant mean change in Hb from pre-treatment levels was observed in the 300 mg daily dosing group. At Weeks 15 to 16, modest, statistically significant mean decreases were observed in the 450 mg daily and 450 mg TIW dosing groups.

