4.5 Safety Endpoints

4.6 Primary Safety Endpoint

Treatment-emergent AEs and treatment-emergent SAEs.

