Abnormal Test Findings – All laboratory test results will be reviewed by the Investigator. The Investigator will utilize his/her judgment in determining if out-of-range laboratory values are clinically significant and will denote this using the abbreviation “CS” on the laboratory report for source documentation. Laboratory tests that are labeled as clinically significant should be reported as AEs, either separately or as part of a description of a symptomatic AE. If there are significant changes in a laboratory report from a previous visit that are determined to be clinically significant, these should also be reported as AEs. Any abnormal laboratory value which requires treatment or further diagnostic testing and/or results in discontinuation from study should be reported as an AE. An expected laboratory abnormality from a condition that is part of the medical history is not considered clinically significant for the purposes of the study unless it represents a worsening of the condition.

Abnormalities in ALT, AST, and Total Bilirubin – Abnormalities in ALT, AST, and total bilirubin should be reported to the Sponsor’s Medical Monitor or CRO designee within 24 hours of awareness as an SAE with ‘other medically important event’ criteria selected, if the following conditions are met:

- New elevation in ALT or AST $>3 \times$ ULN

If new elevations in ALT or AST $>3 \times$ ULN, **without** an elevation of total serum bilirubin $>2 \times$ ULN are identified, the following steps are to be taken:

- Temporary discontinuation of study medication;
- Repeat testing of ALT, AST, alkaline phosphatase (ALP), and total bilirubin, to be completed within 48 to 72 hours to confirm the abnormalities and to determine trend;
- Study medication should not be resumed until monitoring indicates abnormalities have resolved or are stable.

Details on the management of subjects with other ALT and AST abnormalities are further described in [Section 7.1.3](#).

Worsening of Anemia – In this study, it is possible that some subjects may experience a worsening of anemia. As the primary endpoint of this study assesses Hb response, worsening of anemia is captured as part of this efficacy parameter. Worsening of anemia should not be considered an AE unless the worsening of anemia is associated with a cause *other than* the subject’s CKD.

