9.11.1.2 Serious Adverse Events

Each AE is to be classified by the Investigator as SERIOUS or NONSERIOUS. An AE that meets 1 or more of the following criteria/outcomes is classified as serious:

- Death
- Life-threatening (see below for definition)
- In-patient hospitalization or prolongation of existing hospitalization (see paragraph below on hospitalization)
- Persistent or significant disability/incapacity (see paragraph below on disability)
- Congenital anomaly/birth defect
- Is considered a medically important event not meeting the above criteria, but which may jeopardize a subject, or may require medical or surgical intervention to prevent one of the criteria listed in this definition.

In addition to the above criteria for classifying AEs as serious, the following situation will also be classified as serious for purposes of this study:

- Malignancies – Newly diagnosed malignancies or a recurrence of a malignancy should be reported as an SAE with the seriousness criterion “medically important” if no other seriousness criteria are met. However, if a subject develops basal cell carcinoma of skin, squamous cell carcinoma of skin, or cervical carcinoma in situ during the study, or has worsening of these events from Baseline, the Investigator will determine if the event is reported as an AE or SAE.

Serious also includes any other event that the Investigator or Sponsor judges to be serious. If there is any doubt whether the information constitutes an AE or SAE, the information is to be treated as an SAE.

Life-threatening – Any event in which the subject was at immediate risk of death at the time of the event; ‘life-threatening’ does not refer to an event which hypothetically might have caused death if it were more severe. For example, drug-induced hepatitis that resolved without evidence of hepatic failure would not be considered life threatening, even though drug-induced hepatitis of a more severe nature can be fatal.

Hospitalization – Hospitalization is defined as an overnight admission with observation of a minimum of 24 hours. A hospitalization planned before the start of the study for a pre-existing condition that has not worsened during the AE reporting period does not constitute an SAE unless an untoward event occurs related to the procedure (eg, elective hospitalization for a total knee replacement due to a preexisting condition of osteoarthritis of the knee that has not worsened during the course of the study).

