6.12.1 Adverse Events

A treatment-emergent adverse event (TEAE) is one that begins or worsens after treatment initiation. TEAEs will be summarized using the number and percentage of subjects with TEAEs for all subjects in the safety population.

All AEs will be coded by MedDRA. The MedDRA version used for reporting this study will be described in a footnote on AE related outputs. TEAEs will be summarized by SOC and PT for each treatment group. All TEAE summaries will provide the number of subjects reporting at least 1 TEAE. TEAE summaries will be ordered by decreasing pooled percentage for SOC, and PT within SOC.

An overall summary table will show number of subjects with at least 1 of each of the following:

- TEAE
- Drug-related TEAE
- Severe TEAE
- Treatment-emergent SAE
- Drug-related treatment-emergent SAE
- TEAE leading to withdrawal of study drug
- Drug-related TEAE leading to withdrawal of study drug
- Fatal TEAE
- All Deaths: Any deaths reported during the study no matter whether deaths are caused by TEAEs

Summaries by SOC and PT will be provided for the following types of TEAEs:

- TEAE
- TEAE by severity
- Drug-related TEAEs (including all categories for relationship to study medication other than “Unrelated”, as determined by the investigator)
- Treatment-emergent serious adverse event (SAE)

-
- Drug-related treatment-emergent SAE
 - TEAEs leading to withdrawal of study drug
 - Drug-related TEAE leading to withdrawal of study drug
 - Fatal TEAE
 - Adverse events of special interest (AESI) listed on [Appendix E](#)

A summary by treatment group and PT will be presented for TEAEs reported by at least 5% of subjects in either treatment group.

TEAEs will be summarized by 1) worst severity, and 2) worst causality by SOC and PT. For each subject and each PT, the worst severity recorded will be used in the by-severity summaries. Similarly, the worst causality (most related to treatment) attributed will be used in the by-causality summaries. If severity or causality is missing, data will be imputed to the worst category.

Treatment-emergent SAEs and deaths will be summarized by treatment group and overall, including the number and percentage for subject with Treatment-emergent SAEs, number of deaths (all causes, resulting from adverse events). Summary by SOC and PT will include subjects affected by Treatment-emergent SAEs, occurrence (all, causally related to treatment), number of death (all causes), and deaths causally related to treatment.

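### The AE exemption for CKD-attributed worsening of anemia has no exception for serious events and conflicts with other reporting rules, so such events can be left out of the primary safety endpoint

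*Protocol*

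**What the plan says.** Protocol 9.11.1.1, under Worsening of Anemia, tells sites that "Worsening of anemia should not be considered an AE unless the worsening of anemia is associated with a cause" other than the subject's CKD. The reason given is that Hb response is the primary endpoint, so that "worsening of anemia is captured as part of this efficacy parameter". Nothing in the rule limits it to non-serious cases.

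Protocol 4.6 gives the primary safety endpoint as "Treatment-emergent AEs and treatment-emergent SAEs". Protocol 9.11.1.2 defines seriousness starting from an adverse event: "An AE that meets 1 or more of the following criteria/outcomes is classified as serious". The criteria include a life-threatening course and "In-patient hospitalization or prolongation of existing hospitalization". The same section also provides that "Serious also includes any other event that the Investigator or Sponsor judges to be serious". Protocol 9.11.7 attaches the 24-hour report to SAEs.

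SAP 6.12.1 tabulates TEAEs, treatment-emergent SAEs, fatal TEAEs and "TEAEs leading to withdrawal of study drug" by treatment group. It adds a row for all deaths, whether or not caused by a TEAE. It says nothing about anemia that 9.11.1.1 has kept out of AE reporting.

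**The concern.** Loss of Hb control is the most direct harm of a failed conversion, and only the two vadadustat arms convert. If an admission for severe anemia is not an AE, it cannot enter the SAE comparison that serves as the primary safety endpoint, and it does not trigger expedited reporting. Whether a fall in Hb is put down to CKD or to something else is decided by investigators who know the treatment (Protocol 7.3). If vadadustat subjects lose Hb control more often than Mircera subjects, the omission would favour vadadustat in the SAE table. The IDMC's named key safety data are AEs, vital signs and laboratory values (Protocol 11.11), so it would see low Hb values but might not see the serious event.

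**Working it through.** The plan gives no figure to reproduce on this point. The check compares the clauses and then puts a scale on the risk.

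**Step 1: clauses that keep the event out.**
- 9.11.1.1, Worsening of Anemia: not an AE if attributed to CKD.
- 9.11.1.2: the hospitalization and life-threatening criteria apply to an AE, so an event excluded as an AE does not reach them.
- 9.11.1.1, Medical Diagnoses: symptoms with a common cause are reported under the diagnosis, so symptoms of anemia can fold into the exempt term.
- For contrast, 9.11.1.1 writes an explicit SAE route for new ALT or AST elevations above 3 x ULN, and 9.11.1.2 writes one for malignancy. Neither section writes one for anemia.

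**Step 2: clauses that bring it in.**
- 9.11.1.1, opening definition: worsening of a condition already present is an AE. Every subject enters with anemia of CKD.
- 9.11.1.1, Abnormal Test Findings: a laboratory value that needs treatment, or that leads to discontinuation from the study, is an AE. A Hb value that prompts transfusion or ESA rescue fits this.
- 9.11.1.2: the catch-all for events judged serious, and the instruction to treat doubtful cases as SAEs.
- 9.11.2.2: deterioration of the treated condition is among the causes an investigator may choose for an AE.

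The two sets cannot both be followed. The documents do not say which prevails, nor whether a Hb fall after stopping Mircera has a cause other than CKD.

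**Step 3: does the stated reason for the exemption hold?** The primary variable is mean Hb over Weeks 20 to 26, under a treatment-policy strategy that includes rescue (SAP 6.11.1). Subjects who permanently stop study drug leave the study (Protocol 8.1.2). Missing Hb is imputed under missing at random (SAP Appendix B.3). A fall before Week 20, a transient fall or a fall corrected by rescue need not show in that mean, and it is not a count of serious events in any case.

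**Step 4: where the harm is otherwise visible.**
- Hb below 7, 8, 9 and 10 g/dL (Protocol 4.7; SAP 6.12.2.1): central-laboratory values only.
- Transfusion and ESA rescue (SAP 6.11.4.4): an event counts only from first dose to permanent treatment discontinuation, whereas AE collection continues to the safety follow-up visit (Protocol 9.11.5). Protocol 4.7 makes transfusion a secondary safety endpoint. SAP 5.3 lists it under other efficacy endpoints, and SAP 7 does not record the change.
- Reasons for discontinuation by arm (SAP 6.5), with lack of efficacy as one reason (Protocol 8.1.2).
- All deaths (SAP 6.12.1).

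Each is informative, but none of them counts anemia events that met a seriousness criterion.

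**Step 5: scale.** Protocol 3.4 reports for the 450 mg TIW cohort of the phase 2 hemodialysis study that "19% (6 of 31) of subjects withdrew from the study due to worsening anemia". The proportion is 6/31 = 19.4%. The exact (Clopper-Pearson) 95% limits are the 2.5% point of Beta(6, 26) = 7.5% and the 97.5% point of Beta(7, 25) = 37.5%. The daily-dosing cohorts had 0/30 = 0% and 1/33 = 3.0%.

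**The case against.** The strongest reply is that the text does not shut the door. The catch-all, the doubt rule and the general AE rules in Step 2 each give an investigator a route to report. This stands. A reader might infer that CKD anemia can never be an AE or SAE, and the documents do not support that. What remains is that the catch-all is discretionary, that the doubt rule can be read as choosing between AE and SAE only, and that a specific instruction not to report competes with general ones.

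A reader might also infer that nearly every on-study case would be exempt because Exclusion 1 removes other causes of anemia. That criterion concerns entry. It does not rule out bleeding, iron deficiency or inflammation over 52 weeks.

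A further tempting inference is that the harm goes unmeasured. It does not, as Step 4 shows. Withdrawals for anemia appear in disposition, deaths are tabulated regardless of AE status, and the unblinded IDMC sees laboratory data. Nor can one assert that no hospitalization endpoint exists, because parts of the endpoint and analysis text are redacted.

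Finally, one might multiply 6/31 by about 300 vadadustat subjects (2 x 150) to get 58 withdrawals, with limits of about 22 and 112 (300 x 7.45% and 300 x 37.47%), and then apply a serious fraction. The phase 2 subjects converted from epoetin alfa at 450 mg TIW. Here they convert from Mircera at 600 or 900 mg TIW with titration up to 1200 mg. The documents give no serious fraction, so a count of missing SAEs would be a guess.

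The exemption applies to both arms on paper, so bias arises only if the arms differ in loss of Hb control or in attribution.

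**Conclusion.** The point holds as an internal conflict with a real reporting consequence. On the plain reading of the specific rule, a serious episode of CKD-attributed anemia can be omitted from the TEAE/SAE primary safety endpoint and from 24-hour reporting, and sites may resolve the conflict differently in an open-label trial. The conclusion assumes that at least some sites follow the specific exemption over the general rules. Any effect on the comparison also requires that loss of Hb control, or its attribution to CKD, differs between arms. The phase 2 experience makes the risk foreseeable but does not forecast it, and the number of SAEs affected cannot be estimated. Because the related harms are analysed elsewhere, this is a cheap and worthwhile correction and not a failure of safety monitoring.

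**What to change.** Reconcile 9.11.1.1 with 9.11.1.2 by adding one sentence to the Worsening of Anemia rule: worsening of anemia from any cause that meets a seriousness criterion in 9.11.1.2 is reported as an AE and as an SAE. Keep the exemption for non-serious falls in Hb, and say that for those falls it overrides the general rules on pre-existing conditions and laboratory values. In SAP 6.12.1, tabulate these SAEs by arm.

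This changes reporting only. The cost is one protocol sentence, one table and somewhat more SAE reporting. The arm that loses Hb control more often may show a less favourable SAE count.

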9.11.1.2 Serious Adverse Events

Each AE is to be classified by the Investigator as SERIOUS or NONSERIOUS. An AE that meets 1 or more of the following criteria/outcomes is classified as serious:

- Death
- Life-threatening (see below for definition)
- In-patient hospitalization or prolongation of existing hospitalization (see paragraph below on hospitalization)
- Persistent or significant disability/incapacity (see paragraph below on disability)
- Congenital anomaly/birth defect
- Is considered a medically important event not meeting the above criteria, but which may jeopardize a subject, or may require medical or surgical intervention to prevent one of the criteria listed in this definition.

In addition to the above criteria for classifying AEs as serious, the following situation will also be classified as serious for purposes of this study:

- Malignancies – Newly diagnosed malignancies or a recurrence of a malignancy should be reported as an SAE with the seriousness criterion “medically important” if no other seriousness criteria are met. However, if a subject develops basal cell carcinoma of skin, squamous cell carcinoma of skin, or cervical carcinoma in situ during the study, or has worsening of these events from Baseline, the Investigator will determine if the event is reported as an AE or SAE.

Serious also includes any other event that the Investigator or Sponsor judges to be serious. If there is any doubt whether the information constitutes an AE or SAE, the information is to be treated as an SAE.

Life-threatening – Any event in which the subject was at immediate risk of death at the time of the event; ‘life-threatening’ does not refer to an event which hypothetically might have caused death if it were more severe. For example, drug-induced hepatitis that resolved without evidence of hepatic failure would not be considered life threatening, even though drug-induced hepatitis of a more severe nature can be fatal.

Hospitalization – Hospitalization is defined as an overnight admission with observation of a minimum of 24 hours. A hospitalization planned before the start of the study for a pre-existing condition that has not worsened during the AE reporting period does not constitute an SAE unless an untoward event occurs related to the procedure (eg, elective hospitalization for a total knee replacement due to a preexisting condition of osteoarthritis of the knee that has not worsened during the course of the study).

Disability – Defined as a substantial disruption in a person’s ability to conduct normal life functions.

9.11.2 Classification of an Adverse Event

9.11.2.1 Severity of Event

The Investigator will assess each AE as either mild, moderate, or severe using the following guidelines to describe the maximum severity of the AE:

- Mild: Does not interfere with subject's usual function
- Moderate: Interferes to some extent with subject's usual function
- Severe: Interferes significantly with subject's usual function

Note that a **severe** AE is not necessarily a **serious** AE. For example, a headache may be severe in intensity, but would not be classified as serious unless it met 1 of the criteria for serious events listed above.

9.11.2.2 Relationship to Study Intervention

The causal relationship of the AE to vadadustat or Mircera will be assessed by both the Investigator and the Sponsor.

The assessment of causal relationship to study medication should be evidence-based, and not based on the premise that all AEs are possibly causally related to study medication until proven otherwise.

Examples of evidence that would suggest a causal relationship between the study medication and the AE include the occurrence of an AE that is uncommon and known to be strongly associated with drug exposure (eg, angioedema, hepatic injury, and Stevens-Johnson syndrome) or an AE that is uncommon in the population exposed to the drug.

The causal relationship of the AE is assessed using a binary system, and AEs are classified as either 'related' or 'unrelated';

- Related: There is 'reasonable possibility' that the drug caused the AE. The AE follows a reasonable temporal sequence from the time of drug administration. There is supportive evidence (facts) to suggest a possible causal relationship, irrespective of the degree of certainty between the observed AE and the drug.
- Unrelated: An AE does not follow a reasonable temporal sequence from administration of the product and/or there is no reasonable possibility that the drug caused the AE. This assessment includes situations where the AE is related to other factors such as the subject's clinical state, other therapeutic interventions, or concomitant drugs administered to the subject.

Default assessments using the 'related' category without supportive evidence for a causal relationship to study medication is generally uninformative and do not contribute meaningfully to the development of the safety profile of the drug or to subject protection.

Investigators are encouraged to choose the most plausible cause for the event(s) from the following list: medical history, lack of efficacy/worsening of treated condition, study medication, other treatment (concomitant, or previous), withdrawal of study medication, administration error, protocol-related procedure, others (specify).

9.11.2.3 Expectedness

The Sponsor will be responsible for determining whether an AE is expected or unexpected. An AE will be considered unexpected if the nature, severity, or frequency of the event exceeds the risk information previously described for the study intervention as described in the current Investigator's Brochure.

